11.1.2 Special Situations

A special situation is any incidence of drug exposure during pregnancy or breastfeeding, overdose, off-label use, medication errors, occupational exposure, abuse, misuse or lack of therapeutic effectiveness whilst using the medicinal product. A “special situation” should be collected by the Investigator and reported to the Sponsor whether or not these “special situations” are associated with an AE.

11.1.2.1 Pregnancy and Breastfeeding

Women of childbearing potential/Contraception in males and females

A negative pregnancy test is recommended for all women of childbearing potential prior to treatment with mecasermin. It is also recommended that all women of childbearing potential use adequate contraception during treatment.

Pregnancy

There are no or limited amount of data for the use of mecasermin in pregnant women.

Animal studies are insufficient with respect to reproductive toxicity (see Section 5.3 of Increlex® SmPC [22]). The potential risk for humans is unknown.

This medicinal product should not be used during pregnancy unless clearly necessary.

Pregnancy itself is not regarded as an AE unless there is a suspicion that the medicinal product has interfered with a contraceptive method. If pregnancy occurs whilst using the medicinal product, the outcome of the pregnancy will then need to be collected. This applies irrespective of whether the pregnancy is considered to be related to interference by the medicinal product with a contraceptive method or not.

Details of all pregnancies in female participants and, if indicated, female partners of male participants will be collected from the signing of the ICF and until the end of registry participation and/or one month after delivery.

The Investigator is to report to the Sponsor if they become aware of a pregnancy occurring in the partner of a registry participant. If the female partner gives her consent, the pregnancy outcome should be followed up and reported.

Information regarding any pregnancies must be collected on the AE eCRF **and** the Sponsor Adverse Drug Reaction Form [REDACTED]

Abnormal pregnancy outcomes (e.g. spontaneous abortion, foetal death, stillbirth, congenital abnormalities, ectopic pregnancy) are considered SAEs. If there is an abnormal pregnancy outcome or an AE is reported in the foetus/neonate/child following exposure to a marketed Sponsor's product, attempt to follow-up until the end of registry participation and/or one month after delivery.

The Investigator must instruct all female participants to inform them immediately should they become pregnant whilst using the study medication.

Reports of pregnancy must be reported to the Sponsor within 24 hours of the Investigator's knowledge.

Breastfeeding

Breastfeeding while taking Increlex® is not recommended, because there is insufficient information on the excretion of mecasermin in human milk.

Any use of an Sponsor product during lactation/ breastfeeding must be collected on the AE eCRF and the Sponsor Adverse Drug Reaction Form [REDACTED]

11.1.2.2 Overdose

Acute overdose could lead to hypoglycaemia. Treatment of acute overdose of mecasermin should be directed at alleviating any hypoglycaemic effects. Oral glucose or food should be consumed. If the overdose results in loss of consciousness, intravenous glucose or parenteral glucagon may be required to reverse the hypoglycaemic effects.

Long-term overdose may result in signs and symptoms of acromegaly or gigantism. Overdosing may lead to supraphysiological IGF-1 levels and may increase the risk of benign and malignant neoplasm.

In case of an acute or a chronic overdose, Increlex® must be discontinued immediately. If Increlex® is restarted, the dose should not exceed the recommended daily dosage.

An overdose is defined as any dose higher than the maximum recommended dose in the local label/SmPC, or in the protocol. For products which require gradual titration, any dose (initial or maintenance) which is higher than the recommended regime in the protocol, or labelling text will be assessed as 'overdose'. Overdoses are not considered as AEs however should be reported in the AE eCRF page whether or not they were associated with a clinical event. All overdoses should be reported to the Sponsor within 7 calendar days using the Sponsor Adverse Drug Reaction Form [REDACTED]

11.1.2.3 Off-label Use

Off-label use relates to situations where the medicinal product is used for a medical purpose not in accordance with the terms of the Marketing Authorisation. Off-label use should be reported as AEs in the AE eCRF page whether or not they were associated with a clinical event. All off-label use should be reported to the Sponsor within 7 calendar days using the Sponsor Adverse Drug Reaction Form [REDACTED]

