9.2.9 *Treatment Discontinuation*

If benign or malignant neoplasia develops, Increlex® treatment should be discontinued definitely and appropriate expert medical care sought. If a US patient develops benign neoplasm, Increlex® treatment can continue.

Increlex® treatment may be discontinued in the event of any SAEs, AEs or special situations deemed by the Investigator to warrant treatment discontinuation.

Discontinuation of treatment due to AEs should be distinguished from discontinuation/withdrawal from the registry due to participant/parent decision or end of post-treatment follow up. In all cases due to AEs, the Investigator must ensure that the participant receives appropriate medical follow up and this should be properly documented in the participant's medical records.

All participants discontinuing Increlex® treatment will be followed up in the registry in the post-treatment period (unless consent is withdrawn).

9.3 *Endpoints and Variables*

9.3.1 *Endpoints*

9.3.1.1 *Primary Endpoints*

- Incidence of SAEs (including AESI of neoplasia), targeted AEs, all AEs, deaths and withdrawals due to AEs during Increlex® treatment.

9.3.1.2 *Secondary Endpoints*

- Incidence of SAEs (including AESI of neoplasia), targeted AEs, all AEs, deaths, withdrawals due to AEs, special situations and concomitant medications within the 5-year post-treatment period, overall and in the subset of children and adolescents exposed to Increlex® for at least 3 cumulative years excluding interruptions;
- Incidence of special situations and concomitant medications during Increlex® treatment;
- Changes from baseline for the following effectiveness variables: height SDS, height velocity, body mass index (BMI) SDS, bone age development, pubertal (Tanner) stage;
- Estimation of differences between PAH and FAH;
- Modelisation to identify predictive factors of height SDS change, height velocity, FAH, pubertal (Tanner) stage, bone age development;
- Description of Increlex® therapy exposure (dose and duration) and compliance;
- Description of effectiveness parameters (height SDS, height velocity) according to average dose received and according to dose ranges (e.g. 4 dose ranges (≤ 50 , $]50-80]$, $]80-110]$, $> 110 \mu\text{g/kg BID}$). This analysis will support the description of the lowest effective dose;
- Biological assessments (IGF-1 levels, GH concentrations, serum IGFBP3);
- Genetic test results;

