Descriptive statistics will include number of available data, number of missing data and the following:

- Mean, SD, 95% CIs for means when appropriate, median, quartile, minimum and maximum for continuous variables;
- Frequency count, percentages and 95% CIs when appropriate for categorical nominal variables;
- Both the above for categorical ordinal variables.

Missing data will not be replaced but they will be displayed in all relevant tables.

9.7.2.2 *Participant Inclusion*

Based on the screened population, the proportion of non-included patients will be assessed as well as the reasons for non-inclusion.

9.7.2.3 *Demographic and Other Baseline Characteristics*

Descriptive statistics of demographic and baseline data will be presented for the Registry Population.

Previous/concomitant medications will be summarised by drug categories.

Data on medical history, coded using MedDRA, and previous growth therapy will be summarised.

Information on SPIGFD diagnosis, personal or familial risk factors for neoplasia and genetic test results (deletion/mutation of GH gene, IGF-1 gene, FGF, PTPN11, GHR, D3-GHR, STAT5b, ALS, SHOX, PAPPA2 and any other genetic tests performed, e.g. whole exon sequencing) will be described.

9.7.2.4 *Participant Disposition and Withdrawals*

The numbers and percentages of participants included in the analysis populations will be tabulated overall and by country and site. The reasons for participant exclusions from each of the populations will also be tabulated.

In addition, the number of participants who ended the treatment, withdrew or completed the registry will be presented with the primary reasons for discontinuation.

9.7.2.5 *Primary Analyses*

The primary analyses and summary tables of safety data will be based on the Safety Population (data from the treatment period only).

An overall summary table of AEs during the treatment period (up to 30 days after the last dose) including SAEs, AESI, targeted AEs, all AEs, AEs leading to death and AEs leading to withdrawal will be presented with the number and proportion of participants and the number of events.

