10.3 Insurance

Insurance may be contracted according to local regulatory requirements.

11 MANAGEMENT AND REPORTING OF ADVERSE EVENTS/ADVERSE DRUG REACTIONS AND SPECIAL SITUATIONS**11.1 Definition****11.1.1 Adverse Event****AE Definition**

An AE is any untoward medical occurrence in a patient/participant, administered a medicinal product [Increlex® in this registry] and which does not necessarily have a causal relationship with this treatment.

NOTE: An AE can therefore be any unfavourable and unintended sign (e.g. an abnormal laboratory finding), symptom, or disease temporally associated with the use of the medicinal product, whether or not related to the medicinal product.

Events Meeting the AE Definition

Any abnormal laboratory test results (haematology, clinical chemistry, or urinalysis) or other safety assessments (e.g. electrocardiograms, radiological scans, vital signs measurements), including those that worsen from baseline, considered clinically significant in the medical and scientific judgment of the Investigator (i.e. not related to progression of underlying disease).

Exacerbation of a chronic or intermittent pre-existing condition including either an increase in frequency and/or intensity of the condition.

New condition detected or diagnosed after study treatment administration even though it may have been present before the start of the study.

Signs, symptoms, or the clinical sequelae of a suspected drug-drug interaction.

Signs, symptoms, or the clinical sequelae of a suspected overdose of either study treatment or a concomitant medication. Any instances of overdoses irrespective of whether they are associated with AEs or not must be provided to the MAH with the overdose, duration of overdose and outcome. In addition, all cases of off-label use should also be reported as AEs.

The signs, symptoms, and/or clinical sequelae resulting from lack of effectiveness will be reported as AE or SAE if they fulfil the definition of an AE or SAE. Also, “lack of effectiveness” or “failure of expected pharmacological action” also constitutes an AE or SAE.

Events NOT Meeting the AE Definition

Any clinically significant abnormal laboratory findings or other abnormal safety assessments which are associated with the underlying disease, unless judged by the Investigator to be more severe than expected for the participant's condition.

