The disease/disorder being studied or expected progression, signs, or symptoms of the disease/disorder being studied, unless more severe than expected for the participant's condition.

Medical or surgical procedure (e.g. endoscopy, appendectomy): the condition that leads to the procedure is the AE.

Situations in which an untoward medical occurrence did not occur (social and/or convenience admission to a hospital).

Anticipated day-to-day fluctuations of pre-existing disease(s) or condition(s) present or detected at the start of the study that do not worsen.

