11.1.2.4 Medication Error

Medication error is an unintended failure in the drug treatment process that leads to or has the potential to lead to harm to the participant.

Medication error should be reported as AEs in the AE eCRF whether or not they were associated with a clinical event. All medication error should be reported to the Sponsor within 7 calendar days using the Sponsor Adverse Drug Reaction Form [REDACTED]

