Examples of such events include invasive or malignant cancers, intensive treatment in an emergency room or at home for allergic bronchospasm, blood dyscrasias or convulsions that do not result in hospitalisation, or development of drug dependency or drug abuse.

A suspected or confirmed coronavirus COVID-19 (SARS-CoV-2) infection must be reported as serious (seriousness criteria should be “other medically significant” if no other seriousness criteria are present (e.g. hospitalisation).

Is a suspected transmission of any infectious agent via an authorised medicinal product

Regardless of the above criteria, any additional AEs that the Sponsor or an Investigator considers serious should be immediately reported to the Sponsor. Any onset or recurrence of neoplasia must also be reported as an SAE.

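### Section 11 contradicts itself on whether special situations without a clinical event are adverse events, and it makes every COVID-19 infection serious; both raise primary incidences by an amount the protocol does not let one quantify

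*Protocol*

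**What the plan says.** Section 11.1.1 defines an AE as an untoward medical occurrence. Among the things that do not meet the definition it lists "Situations in which an untoward medical occurrence did not occur". In the same section, under events that do meet the definition, it adds: "In addition, all cases of off-label use should also be reported as AEs".

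The special-situation subsections then diverge:

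- Overdose (11.1.2.2): "Overdoses are not considered as AEs however should be reported in the AE eCRF page".
- Off-label use (11.1.2.3): "Off-label use should be reported as AEs in the AE eCRF page whether or not they were associated with a clinical event".
- Medication error (11.1.2.4): "Medication error should be reported as AEs in the AE eCRF whether or not they were associated with a clinical event".
- Abuse (11.1.2.6) and misuse (11.1.2.7) carry the same instruction, with the same clause about a clinical event.
- Occupational exposure (11.1.2.5) is also to be reported as an AE, without that clause.

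On seriousness, 11.1.3 says: "A suspected or confirmed coronavirus COVID-19 (SARS-CoV-2) infection must be reported as serious". Where no other criterion is met, the case is to be classed as otherwise medically significant.

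The primary endpoint (9.3.1.1) is: "Incidence of SAEs (including AESI of neoplasia), targeted AEs, all AEs, deaths and withdrawals due to AEs during Increlex® treatment". The primary overall summary table (9.7.2.5) "will be presented with the number and proportion of participants and the number of events". Special situations are a separate secondary endpoint (9.3.1.2) with a separate summary table (9.7.2.6).

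**The concern.** A site cannot follow all of these instructions at once. A participant treated off-label who has no symptom or finding has no AE under the definition, but has one under 11.1.2.3 and the off-label sentence of 11.1.1. An overdose without consequences goes on the same eCRF page and is expressly not an AE.

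This matters because the same section decides what sites record as AEs, and all AEs are a primary endpoint component. If the literal instruction is followed, the proportion of participants with any AE, and the number of events, include records in which nothing medical happened. The COVID-19 rule has a similar effect one level up: an infection that meets no ordinary seriousness criterion still counts as an SAE, so the overall SAE incidence depends partly on a reporting convention.

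**Working it through.** **Step 1: the rules side by side.**

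| Situation | Section | Goes on AE page? | Is it an AE without a clinical event? |
|---|---|---|---|
| General definition | 11.1.1 | – | No |
| Pregnancy | 11.1.2.1 | Yes | No, unless interference with contraception is suspected |
| Overdose | 11.1.2.2 | Yes | No |
| Off-label use | 11.1.1, 11.1.2.3 | Yes | Yes |
| Medication error | 11.1.2.4 | Yes | Yes |
| Occupational exposure | 11.1.2.5 | Yes | To be reported as an AE; clinical event not mentioned |
| Abuse | 11.1.2.6 | Yes | Yes, although its definition presupposes harmful effects |
| Misuse | 11.1.2.7 | Yes | Yes |

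For pregnancy and overdose the protocol separates being recorded on the AE page from being an AE. For the next five categories it does not. Elsewhere it treats the two as distinct: 9.3.2.2 collects, for each special situation, whether it led to an AE, and 11.1.2 and the table in 11.2.2 require reporting whether or not an AE is associated.

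**Step 2: does it reach the primary analysis?** 9.3.1.1 and 9.7.2.5 include all AEs and SAEs on treatment, up to 30 days after the last dose. No sentence in 9.7 excludes event-free entries or COVID-19 cases that are serious only by rule. On the literal reading both are counted.

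**Step 3: direction and possible size.** The protocol states no AE or SAE rate, so there is no planned figure to reproduce. Let p be the proportion with a genuine clinical AE (or an SAE on the ordinary criteria). Let q be the share of the remaining participants who have only an event-free record (or only a COVID-19 case serious by rule). Then

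observed proportion = p + (1 − p) × q,

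which is never below p. All values of p and q here are assumptions:

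| Any AE: p | q = 2% | q = 10% | q = 30% |
|---|---|---|---|
| 50% | 51.0% | 55.0% | 65.0% |
| 70% | 70.6% | 73.0% | 79.0% |
| 90% | 90.2% | 91.0% | 93.0% |

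| SAE: p | q = 2% | q = 5% | q = 10% |
|---|---|---|---|
| 5% | 6.9% | 9.8% | 14.5% |
| 10% | 11.8% | 14.5% | 19.0% |
| 20% | 21.6% | 24.0% | 28.0% |

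For example, 0.70 + 0.30 × 0.10 = 0.73, and 0.10 + 0.90 × 0.05 = 0.145. The effect on any-AE incidence is small when the base is high. The relative effect on SAE incidence can be larger because its base may be low. The count of events rises by one for every such AE record, whatever p is.

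**The case against.** The strongest reply is that the special-situation subsections are recording and pharmacovigilance rules, not analysis rules. Special situations have their own variable, endpoint, table and reporting row, and 9.7.2.1 leaves table detail to a separate SAP, which was not available here and might filter these records. It can also be said that the non-AE list illustrates its exclusion with social or convenience hospital admission, and that 11.1.1 places off-label use among events meeting the definition. Part of this stands: inflation follows from the literal reading and is not an established result. But the wording says these items are reported as AEs, and the overdose subsection shows that the protocol knows how to say otherwise. A SAP that dropped them would override an explicit instruction on a primary component; one that kept them would contradict the general definition.

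A reader might infer more than the documents support:

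- **A large, quantified inflation.** Nothing supports a particular off-label share. The current criteria tie eligibility to the local label, and off-label participants enrolled before Amendment 6 are described as continuing for safety data in the post-treatment period, although their earlier treatment data could still count. For COVID-19, collection began in December 2008 and the primary table covers treatment plus 30 days, so participants whose treatment ended before the pandemic cannot contribute. A high COVID-19 share of the whole Safety Population is implausible.
- **A diluted neoplasia signal.** Neoplasia, targeted AEs, deaths and AEs leading to withdrawal have their own lines, and extra AE records do not change the participant denominator.
- **Double counting.** A record may appear in both an AE table and the special-situations table, but the two are not added together.
- **Loss of comparability with earlier interim reports.** Those reports are not at hand, and the protocol does not show when either rule began.

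The records also stay identifiable through the SOC/PT tables, the listings and the assigned seriousness criterion, so no information is lost.

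**Conclusion.** The contradiction within Section 11 is real and bears on a primary endpoint component. If the text is followed as written, the any-AE incidence is biased upward by event-free off-label use, medication error, occupational exposure and misuse. Abuse adds little, since its definition already requires harm. The COVID-19 rule is a weakness in the endpoint definition rather than a contradiction, and it raises the overall SAE incidence. The direction of both effects is certain on the literal reading; the size cannot be derived from the protocol, and the tables above are illustrations only. AESI (neoplasia) and targeted-AE incidences are not affected. This should be fixed, but it does not undermine the registry's main safety question.

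**What to change.** 1. In the off-label sentence of 11.1.1 and in 11.1.2.3 to 11.1.2.7, adopt the approach already used for overdose: enter the item on the AE page, report it to pharmacovigilance as a special situation, and count it as an AE only if a clinical event occurred.
2. In 9.7.2.5 and 9.7.2.6, state that special situations without a clinical event appear only in the special-situations table. Identify them with the variable in 9.3.2.2 that records whether the situation led to an AE.
3. Present overall SAE incidence with and without COVID-19 cases whose only seriousness criterion is the mandatory classification as otherwise medically significant.

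The cost is a wording change in Section 11, a sentence in each of two analysis sections, one analysis flag and one extra display. Existing records can be reclassified from fields already collected. What sites report to the sponsor, and how quickly, stays the same.

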11.1.2.4 Medication Error

Medication error is an unintended failure in the drug treatment process that leads to or has the potential to lead to harm to the participant.

Medication error should be reported as AEs in the AE eCRF whether or not they were associated with a clinical event. All medication error should be reported to the Sponsor within 7 calendar days using the Sponsor Adverse Drug Reaction Form [REDACTED]

11.1.2.5 Occupational Exposure

Occupational exposure refers to the exposure to a medicinal product, as a result of one's professional or non-professional occupation. It does not include the exposure to one of the ingredients during the manufacturing process before the release as finished product.

Occupational exposure should be reported as AEs in the AE eCRF. All occupational exposure should be reported to the Sponsor within 7 calendar days using the Sponsor Adverse Drug Reaction Form [REDACTED]

11.1.2.6 Abuse

Abuse corresponds to the persistent or sporadic, intentional excessive use of a medicinal product, which is accompanied by harmful physical or psychological effects.

Abuse should be reported as AEs in the AE eCRF page whether or not they were associated with a clinical event. All abuse should be reported to the Sponsor within 7 calendar days using the Sponsor Adverse Drug Reaction Form [REDACTED]

11.1.2.7 Misuse

Misuse refers to situations where the medicinal product is intentionally and inappropriately used not in accordance with the terms of the Marketing Authorisation.

Misuse should be reported as AEs in the AE eCRF page whether or not they were associated with a clinical event. All misuse should be reported to the Sponsor within 7 calendar days using the Sponsor Adverse Drug Reaction Form [REDACTED]

